1.1. Trial Objectives

Primary Objective

The primary objective is to establish the safety profile of daratumumab when given in combination with Len/Dex in subjects with relapsed or relapsed and refractory multiple myeloma.

Secondary Objectives

- To evaluate the efficacy of daratumumab when given in combination with Len/Dex in subjects with relapsed or relapsed and refractory multiple myeloma.
- To evaluate the pharmacokinetic (PK) profile of daratumumab when given in combination with Len/Dex in subjects with relapsed or relapsed and refractory multiple myeloma.
- To assess the immunogenicity of daratumumab.

1.2. Trial Design

This is an open-label, dose-escalation, multicenter Phase 1/2 safety study of daratumumab in combination with Len/Dex in the treatment of subjects with relapsed or relapsed and refractory multiple myeloma. The dose escalation portion of the study (Phase 1) will be a standard 3 + 3 design and will evaluate daratumumab, at doses from 2 mg/kg up to a maximum of 16 mg/kg, in combination with Len/Dex in 28-day treatment cycles. The standard "3 + 3" rules for dose escalation will be applied, However, if the study sites have identified 4 eligible subjects to start a new dose level, all 4 subjects may be enrolled. The maximum tolerated dose (MTD) will be defined as the highest dose of the combination regimen at which less than 33% of subjects experience dose-limiting toxicity (DLT). A recommended Phase 2 dose (RP2D) will be determined during Phase 1. The MTD or any dose evaluated in the range of 2 to 16 mg/kg of daratumumab may be considered as the RP2D based on available safety, PK/pharmacodynamic, and efficacy data from Phase 1. The RP2D could be selected before escalation to or completion

5

of the 16 mg/kg cohort. Once the RP2D is determined, the expansion (Phase 2) will open to further explore the safety and efficacy of the RP2D in approximately 30 subjects.

For Phase 1 and Phase 2 of the study there will be a Screening Period followed by the first 2 treatment cycles and will consist of weekly daratumumab infusions, totaling 4 infusions during each 28-day cycle. Cycles 3 through 6 will consist of daratumumab infusions administered every other week; Cycle 7 and all subsequent cycles will consist of monthly daratumumab infusions. The combination treatment may continue until the subject experiences disease progression or unacceptable toxicity, whichever comes first. For Phase 1 only, to minimize the risk of cytokine release syndrome, the first infusion of the first cycle will be preceded by a predose infusion the day before the scheduled full-dose infusion. The predose infusion will be 10% of the full dose, but will never be more than 10 mg in total dose. Further measures to prevent cytokine release syndrome will include premedication with antihistamines, acetaminophen, and dexamethasone before each daratumumab infusion (both predose and full dose).

For Phase 1 and Phase 2, lenalidomide will be administered at a dose of 25 mg orally (PO) on Days 1 through 21 of each 28-day cycle, and dexamethasone will be administered at a total dose of 40 mg weekly. As of Amendment 6, subjects older than 75 years or underweight (body mass index [BMI] <18.5), the dexamethasone dose may be administered at a dose of 20 mg weekly. On weeks when daratumumab is administered the 20 mg dose should be administered as the premedication per protocol. Details on the dosing regimens for Len/Dex are provided in protocol.

During Phase 1, decisions to escalate the dose of daratumumab for the next cohort will be based on the safety data obtained from the 3 (+ 3) subjects in the previous cohort during their first treatment cycle (28 days). The Independent Data Monitoring Committee (IDMC) will evaluate all safety data (including SAEs, AEs, and laboratory data) after each cohort completes Cycle 1. The third subject in the cohort must have received all 4 full doses of daratumumab, and data from an observation period of 6 days after the last infusion must be available for the IDMC to review. Based on the results presented in these safety profiles, the IDMC will recommend to the sponsor if it appears safe to escalate the dose. The recommendation will be discussed and confirmed by the sponsor, who will ultimately decide if dose escalation will occur. Subjects who discontinue the study during the first cycle for reasons other than a DLT will be replaced.

The IDMC and sponsor may decide to implement intermediate doses to ensure subject safety and better define the RP2D. The RP2D, as defined by the IDMC and sponsor, or the maximum dose tested will be the dose level at which subjects will be treated in Phase 2 of the study.

In both phases of the study, investigational product will be administered per schedule up to disease progression, intolerability, withdrawal, death, or unless otherwise indicated by IDMC. Daratumumab may be continued until investigator's or sponsor's recommendation of discontinuation, the subject's decision to discontinue for any reason, or disease progression.

1.3. Statistical Hypotheses for Trial Objectives

For both two phases, the primary endpoint is adverse event; therefore, no formal statistical hypothesis testing is planned.

1.4. Sample Size Justification

No formal sample size determination was performed for Phase 1 of this study because a standard dose escalation study design of 3 + 3 subjects in each cohort was chosen for Phase 1.

For Phase 2, it is assumed that lenalidomide + dexamethasone would achieve an overall response rate (ORR) of 50% in the targeted population. With a two-sided alpha of 0.10 and assuming that the addition of daratumumab improves the ORR to 75%, a sample size of approximately 30 subjects would achieve 89% power to detect such a difference. If the addition of daratumumab can improve the ORR to 80%, this sample size would achieve 97% power to detect such a difference.

1.5. Randomization and Blinding

Not applicable.

2. GENERAL ANALYSIS DEFINITIONS

2.1. Visit Windows

The baseline value is defined as the closest non-missing value taken on or prior to the first dosing date (including time if time is available).

Study day is defined as date of assessment – first dosing date + 1 for any assessment done on or after first dosing date; otherwise, study day is defined as date of assessment – first dosing date.

Day 1 is the first dosing date.

Unless otherwise specified, data to be analyzed or presented over time will be presented by cycle, day, and time point (as appropriate) that are recorded in the eCRF.

However, assessment performed in the same cycle may not be well aligned in time scale for different subjects due to possible cycle delays. To address this, the following by-week windowing rule will be used.

Time Interval	Time Interval	
(Week)	(Study Day)	Target Time Point
Baseline	Day ≤ 1	1
Week 1	$2 \le \text{Day} \le 11$	8
Week 2	$12 \le \text{Day} \le 18$	15
Week 3	$19 \le \text{Day} \le 25$	22
Week 4	$26 \le \text{Day} \le 32$	29
Week 5	$33 \le \text{Day} \le 39$	36
Week 6	$40 \le \text{Day} \le 46$	43
Week 7	$47 \le \text{Day} \le 53$	50
Week 8	$54 \le \text{Day} \le 63$	57
Week 10	$64 \le \text{Day} \le 77$	71
Week 12	$78 \le \text{Day} \le 91$	85
Week 14	$92 \le \text{Day} \le 105$	99
Week 16	$106 \le \text{Day} \le 119$	113
Week 18	$120 \le \text{Day} \le 133$	127
Week 20	$134 \le \text{Day} \le 147$	141
Week 22	$148 \le \text{Day} \le 161$	155

Week 24 Week 28 Week 32 Week 36	$162 \le Day \le 182$ $183 \le Day \le 210$ $211 \le Day \le 238$ $239 \le Day \le 266$	169 197 225 253
 Week 4*(X-1)	$(X-1)*28 - 13$ $\leq Day \leq$ (X-1)*28 + 14	(X-1)*28 + 1

If more than 1 assessment falls within the same time window, the one closest to the target day will be considered as scheduled and others as unscheduled #1, #2, etc., achieving 1 assessment per time interval.

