IgA, IgM, IgG (M-component serum)	X	X			X		X				X		X	X	X	
M-component (24-hour urine sample) ^o	X	X			X		X				X		X	X	X	
Free light chain kappa, lambda, and ratio (serum)	X	X			X		X				X		X	X	X	
New cancer assessment ^p																X

Key: CT = computed tomography; d = day; ECG = electrocardiogram; ECOG = Eastern Cooperative Oncology Group; EOT = End of Trial; FU = Follow-up; Ig = immunoglobulin; w = week

- All cycles are 28-day cycles; the first visit of a cycle should be 4 weeks after the start of the previous cycle.
- Informed consent may be obtained outside of the Screening Visit window, ie, before the Screening Visit date.
- Signs and symptoms (nonserious adverse events) occurring between the Screening Visit (before the first infusion) and the first study drug treatment at Cycle 1 Visit 1 should be recorded as medical history.
- d Vital signs, defined as blood pressure, pulse, and temperature will be measured at the following time points on days when daratumumab infusions are given: just before the planned infusion start time; at 15-minute intervals during the first 2 hours of the infusion; at 60-minute intervals after the first 2 hours during the infusion; at the end of the infusion; and after the infusion at 10 minutes, 30 minutes, 1 hour, and 2 hours.
- Electrocardiograms (ECGs) will be performed at the Screening Visit (before the first infusion), before and after each daratumumab infusion, and at the EOT Visit. Three baseline ECGs should be performed before the first infusion of study drug. Before the ECGs are recorded, the subjects must be resting in a horizontal position for at least 20 minutes
- The computed tomography scan and bone marrow biopsy/aspirate may have been performed within 6 weeks before Cycle 1 Visit 1.
- To be completed as indicated to confirm response at the subsequent bone marrow biopsy visit or to investigate new symptoms, and at physician discretion.
- h Unless otherwise stated, all blood and urine samples must be taken before administration of daratumumab.
- Blood samples drawn for biochemistry assessments will be analyzed for the following: sodium, potassium, blood urea nitrogen, creatine, aspartate aminotransferase, alanine aminotransferase, alkaline phosphatase, bone-specific alkaline phosphatase, albumin, calcium, glucose, total creatinine kinase, total bilirubin, lactic dehydrogenase, uric acid, β₂-microglobulin, and C-reactive protein.

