9.2.1.4. Electrocardiogram

Electrocardiograms will be performed at the Screening Visit or before the first infusion and before and after each infusion for Phase 1 (Table 1) and before and after the daratumumab infusion on Day 1 of each Cycle for Phase 2 (Table 2) to investigate possible Table 1 cardiac effects of daratumumab and/or combination therapy with special attention to possible QT and corrected QT interval disturbance. A follow-up ECG will be performed at the EOT Visit. Any abnormal ECG finding that meets the criteria for an AE or SAE must be recorded and reported as such.

The ECGs will be recorded digitally at the sites by using the standard 12-leads. Three baseline ECGs should be performed before the first infusion of the study drug as described in the ECG Specification Manual. An overall interpretation of the ECGs will be performed by the investigator or by a local site cardiologist if the task is delegated by the investigator.

Before the ECGs are recorded, the subjects should be resting in a horizontal position for at least 20 minutes. If any irregularity is observed or occurs during the ECG (eg, vomiting, cough), the occurrence should be recorded in the eCRF with a description and time of the event. In these cases, the ECG may be recorded again.

The date, time, and overall interpretation of the ECG will be recorded in the eCRF, along with blood pressure and heart rate.

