11.1. Subject Information

The 2 phases of this study will be analyzed separately. When appropriate, all subjects who are treated with daratumumab may be combined together for comprehensive safety assessment.

Variables will be estimated by using descriptive statistics. Continuous variables will be summarized by using the number of observations (n), mean, standard deviation, median, minimum, and maximum, where n denotes the number of subjects with available data. Categorical variables will be summarized by using n and percentages, where the calculation of the percentages will be based on the number of subjects in the population (N) and the number of subjects with available data (n). Results will be presented by cohort as well as by all subjects combined.

The latest available measurements before study drug administration will serve as baseline values.

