2.3.4. QT Evaluable Analysis Set

QT evaluable analysis set in each phase consists of all enrolled patients who had at least one non-zero dose of daratumumab, and had a baseline Electrocardiogram (QT) evaluation and a post-baseline QT evaluation.

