6.5. Electrocardiogram

Frequencies of overall interpretation of ECG results (normal, abnormal and clinically significant, abnormal and not clinically significant) over time will be provided.

All the ECG results and the change from baseline overtime will be listed. QTcB/QTcF intervals and the change from baseline overtime will be summarized for each phase using the QT evaluable analysis set.

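### QTc change from baseline uses one of the three required baseline ECGs; averaging all three would cut its variance, by 33% at most

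*SAP*

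**What the plan says.** Protocol section 9.2.1.4 sets the collection rule: "Three baseline ECGs should be performed before the first infusion of the study drug as described in the ECG Specification Manual". The ECG footnotes to the Phase 1 schedule (Table 1) and the Phase 2 schedule (Table 2) repeat it: "Three baseline ECGs should be performed before the first infusion of study drug".

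The analysis rule is general and covers all variables. SAP section 2.1 states: "The baseline value is defined as the closest non-missing value taken on or prior to the first dosing date". Where several assessments fall in one window (the Baseline window is Day 1 or earlier), the same section keeps one: "the one closest to the target day will be considered as scheduled and others as unscheduled #1, #2, etc., achieving 1 assessment per time interval". Protocol section 11.1 agrees in substance: "The latest available measurements before study drug administration will serve as baseline values".

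Two SAP sections deal with ECGs specifically, and neither changes this rule. Section 2.3.4 requires only that a subject "had a baseline Electrocardiogram (QT) evaluation and a post-baseline QT evaluation". Section 6.5 plans the output: "QTcB/QTcF intervals and the change from baseline overtime will be summarized for each phase using the QT evaluable analysis set". Neither document says that the three baseline ECGs are averaged.

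**The concern.** Safety is the primary objective, and protocol section 9.2.1.4 names QT and corrected QT as a particular focus of the ECG monitoring. A replicated baseline is useful for QTc change because error in the baseline enters every later change score for that subject. The protocol asks subjects for the replicates, but the analysis rule then takes a single value.

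The groups are small (about 30 subjects in Phase 2, 42 to 58 in the whole study), so the spread of the QTc summary matters to anyone reading it. The rule is also incomplete for replicates. If the three ECGs carry the same date and time, or a time is missing, it does not say which one is closest.

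**Working it through.** **The plan's own figure.** There is none to reproduce. The documents give no QTc standard deviation, replicate correlation or precision target. The 89% and 97% power figures concern the overall response rate and do not depend on QTc.

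**Inputs from the documents.**
- Baseline ECGs required: 3, in both phases (protocol section 9.2.1.4, Tables 1 and 2).
- Baseline values used: 1 (SAP section 2.1, protocol section 11.1).
- Phase 2 size: about 30 (SAP section 1.4).

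**Assumed quantities.**
- s: within-subject error SD of one ECG, the same before and after dosing.
- ρ: error correlation among the baseline replicates.
- τ: SD between subjects of the true QTc change.
- The post-baseline value is one ECG, and its error is independent of the baseline errors.

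**Formula.** For one post-baseline ECG minus the mean of m baseline ECGs:

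Var(change) = τ² + s² + s²[1 + (m − 1)ρ]/m

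- m = 1 (the plan): τ² + 2s²
- m = 3 (mean of three): τ² + s² + s²(1 + 2ρ)/3
- Saving: s² · 2(1 − ρ)/3
- Proportional cut: [2(1 − ρ)/3] / (τ²/s² + 2)

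**Results, in units of s².**

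| ρ | τ²/s² | Variance, one ECG | Variance, mean of three | Cut in variance | Cut in SD |
|---|---|---|---|---|---|
| 0 | 0 | 2 | 1.333 | 33.3% | 18.4% |
| 0 | 1 | 3 | 2.333 | 22.2% | 11.8% |
| 0.6 | 0 | 2 | 1.733 | 13.3% | 6.9% |
| 0.6 | 1 | 3 | 2.733 | 8.9% | 4.6% |
| 0.9 | 0 | 2 | 1.933 | 3.3% | 1.7% |
| 0.9 | 1 | 3 | 2.933 | 2.2% | 1.1% |

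The first row is the ceiling for non-negative ρ: a positive ρ or any true variation in change lowers the cut. The cut stays above zero for every ρ below 1.

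**Scale in milliseconds.** This is an illustration at the ceiling (ρ = 0, τ = 0), with s assumed to lie between 6 and 12 ms and n = 30. The 95% half-width for mean change is 1.96 · s · √2/√30 with one baseline ECG and 1.96 · s · √(4/3)/√30 with the mean of three.
- s = 6: 3.0 ms becomes 2.5 ms.
- s = 12: 6.1 ms becomes 5.0 ms.

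**The case against.** The strongest reply is that nothing in the plan depends on this. The primary endpoint is adverse-event incidence, SAP section 5.1.1 plans no formal test, and section 6.5 describes QTc without a threshold, outlier category or decision rule. Protocol and SAP also agree on using one latest value, so there is no contradiction between them. All of this stands. It limits the point to a gain in precision, but it does not make one value as good as three.

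Some stronger readings are tempting and do not hold.
- A reader might infer that two of the three recordings are lost. They are not: section 2.1 labels surplus assessments unscheduled, and section 6.5 lists all ECG results. They are only left out of the change score.
- A reader might infer that QTc change is biased, or distorted by regression to the mean. Choosing a replicate by its timing, not its value, does not bias the mean change if the replicates share one expected value. Section 6.5 also plans no baseline-conditioned or categorical QTc analysis in which regression to the mean would mislead.
- A reader might take 33% as the expected gain. With neither ρ nor τ in the documents, it is only an upper limit.
- A reader might average every ECG before the first infusion. A Screening ECG can be up to 21 days old, and exclusion criterion 9 rejects subjects with a screening QTcF above 470 ms (females) or 450 ms (males). Adding that ECG would mix in a value that had to pass a limit. The documents do not say whether it counts among the three.

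Two uncertainties remain. The ECG Specification Manual may describe how replicates are handled, but the SAP does not refer to it. The eCRF fields named in protocol section 9.2.1.4 do not include interval values. The planned QTc summary implies that some are captured, but not that all three baseline sets are.

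**Conclusion.** The point holds as a modest improvement in an analysis choice. As written, QTcB/QTcF change is computed from one of three required baseline ECGs, and the mean of the three would be more precise for any replicate correlation below 1. The reduction in variance lies between near zero and 33%, depending on values that the documents do not give. The calculation rests on equal single-ECG variance before and after dosing, a single post-baseline ECG per change score and independence of pre-dose and post-dose errors. No stated sample size, power or primary safety conclusion is affected.

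**What to change.** Add to SAP section 6.5:

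> As an exception to SAP section 2.1 and protocol section 11.1, the baseline for ECG intervals (QTcB, QTcF) is the mean of the non-missing values from the three protocol baseline ECGs taken before the first daratumumab infusion (in Phase 1, the predose infusion). A separate, earlier Screening ECG is not included unless it is one of those three.

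Naming protocol section 11.1 matters because the SAP would otherwise depart from the protocol's baseline definition without saying so. Naming the first daratumumab infusion matters because SAP section 1 counts lenalidomide and dexamethasone as study drug, and either may be given before that infusion.

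The cost is this short addition, a small programming change and one data check: that interval values from all three baseline ECGs are in the database. No new visits or recordings are needed. If values from only one ECG were captured, the gain is not available, and the SAP should say which ECG serves as baseline.

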2.2. Pooling Algorithm for Analysis Centers

Not applicable.

2.3. Analysis Sets

2.3.1. Efficacy Analysis Set(s)

The following efficacy populations will be used for Phase 2.

Intent-to-Treat (ITT) population: all enrolled patients who signed the informed consent during Phase 2. This is the analysis population for all efficacy endpoints.

Per-protocol (PP) population: all ITT patients who met all entry criteria and did not have any major protocol deviations that would significantly impact efficacy evaluation during Phase 2. The PP population will be used as sensitively analyses for the selected efficacy endpoints.

2.3.2. All Treated Analysis Set

All treated analysis set includes all enrolled patients who received at least one non-zero dose of any study drug during Phase 1. This population will be used for all efficacy and safety analyses in Phase 1.

2.3.3. Safety Analysis Set

The safety analysis set includes all enrolled patients who received at least one non-zero dose of any study drug during Phase 2. This population will be used for all safety analyses in Phase 2.

2.3.4. QT Evaluable Analysis Set

QT evaluable analysis set in each phase consists of all enrolled patients who had at least one non-zero dose of daratumumab, and had a baseline Electrocardiogram (QT) evaluation and a post-baseline QT evaluation.

2.4. Definition of Subgroups

Not applicable for Phase 1.

For Phase 2, exploratory subgroup analyses may be performed for selected efficacy endpoints:

Subgroup	Category	Analysis Type
Age	$18 - < 65, 65 - < 75, \ge 75$	E,S
Sex	Female, Male	E,S
Race	White, Other (excluding unreported)	Е
ISS staging	I, II, III	Е
Number of prior lines of		Е
therapy	1 line, 2-3 lines, >3 lines	
Refractory to PI	Yes	Е
Refractory to last line of prior		
therapy	Yes	E
Prior exposure to lenalidomide	Yes, No	Е
Type of myeloma	IgG vs. non-IgG	Е
	Creatinine clearance: $<30, 30 - <60, \ge 60$	
Renal function	mL/min	E
Bone marrow % plasma cells	≤30, 30<- ≤60, >60	Е

E: efficacy (ORR); S: safety (TEAE)

2.5. Imputation of Missing Data

2.5.1. Adverse Event Start/End Date

If the onset date of an adverse event is missing completely or partially, the following imputation rules will be used.

- When month and year are present and the day is missing. If the onset month and year are the same as the month and year of first dose date, the day of first dose or the day-component of the AE end date (possibly imputed) is imputed, whichever is earlier; If the onset month and year are not the same as the month and year of first dose, the first day of the month is imputed.
- When only a year is present or no components of the onset date are present. If the onset year is the same as the year of first dose, if AE end date is available and is prior to first dose date, the day and month of AE end date are imputed. Otherwise, the day and month of the first dose date are imputed. If the onset year is different from the year of first dose, the 1st of January is imputed.
- If the onset date is completely missing, the first dose date is imputed as the onset date.
- No imputation will be done for partial or missing AE onset time.

If the end date of an adverse event is missing completely or partially, the following imputation rules will be used.

- If month and year are present and the day of the month is missing, the last day of the month is imputed.
- If only a year is present, the 31st of December is used.
- If the imputed date is later than the date of death (if available) after imputation, the date of death will be used as the imputed date.
- No imputation will be done for partial or missing AE end time.

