2.6.12. Treatment Emergent Adverse Events

Treatment emergent adverse events (TEAEs) are defined as any AE with onset date and time on or after that of the first dose of study drug infusion through 30 days after the last dose of study drug or the day prior to start of subsequent therapy, whichever is earlier; or any AE that is considered related to (probably, or possibly related) study drug regardless of the start date of the event. AEs with missing or partial onset date and time will be considered as treatment-emergent unless the onset date and time of an AE can be determined as earlier than that of the first dose, or later than 30 days after last infusion .

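### The SAP rule for an adverse event with a missing onset day compares bare day numbers and can date an on-treatment event before the first dose

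*SAP*

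**What the plan says.** SAP 2.5.1 (Adverse Event Start/End Date) imputes onset dates in bullets.

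- **Day missing.** The trigger is "If the onset month and year are the same as the month and year of first dose date". In that case "the day of first dose or the day-component of the AE end date (possibly imputed) is imputed, whichever is earlier". Nothing requires the end date to lie in the same month as the first dose, or before it.
- **Only a year, or nothing, recorded.** When the onset year matches the first-dose year, "if AE end date is available and is prior to first dose date, the day and month of AE end date are imputed". Failing that, the first dose supplies both components. This bullet compares full dates.
- **Completely missing.** "If the onset date is completely missing, the first dose date is imputed as the onset date". No exception is given for an event that ended earlier.

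For end dates the same section says: "If month and year are present and the day of the month is missing, the last day of the month is imputed".

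SAP 2.6.12 defines a treatment-emergent event as "any AE with onset date and time on or after that of the first dose of study drug infusion", up to 30 days after the last dose or the day before subsequent therapy. It adds any event rated related, whatever its start date. Its fallback begins "AEs with missing or partial onset date and time will be considered as treatment-emergent unless the onset date and time of an AE". The exception it goes on to make is for an onset shown to fall before the first dose, or more than 30 days after the last infusion. It does not say whether an imputed date may be used for that decision.

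**The concern.** A day number has no order in time unless the months agree. An event that starts in the first-dose month and ends in a later month often ends on a smaller day number than the day of first dose. The day-missing bullet then carries that smaller number back into the first-dose month and produces an onset before any drug was given. The year-only bullet makes the correct comparison, so the day-missing bullet looks like a drafting slip rather than a choice.

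The pre-dose date will usually be false. Protocol 9.2.1.2 and 12.6.1 send nonserious events between screening and first study drug to medical history. A nonserious event record with onset in the first-dose month is therefore normally an on-treatment event.

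Adverse event incidence is the primary endpoint (Protocol 9.3), and SAP 6.1 summarizes only treatment-emergent events unless otherwise specified. Onset dates also feed the Kaplan-Meier plot of time to first infection (SAP 6.1.2.2), the listings, and the rule that links consecutive records of the same preferred term (SAP 2.6.13).

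**Working it through.** The plan gives no figure to reproduce here. The check applies the rule to dates.

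**Formulas**

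- As written: imputed onset day = min(day of first dose, day of AE end date), placed in the month and year of first dose.
- With full dates compared: imputed onset = AE end date if that date is before the first dose date; otherwise the first dose date.

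**Worked cases (onset day missing, onset month = first-dose month)**

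| First dose | AE end | As written | Shift from first dose | Full dates |
|---|---|---|---|---|
| 25 March | 3 April | min(25, 3) = 3, so 3 March | 22 days early | 25 March |
| 20 March | 5 April | min(20, 5) = 5, so 5 March | 15 days early | 20 March |
| 20 March | 25 March | min(20, 25) = 20, so 20 March | none | 20 March |
| 20 March | 10 March | min(20, 10) = 10, so 10 March | 10 days before, correctly | 10 March |
| 30 January | February, day missing, imputed as 28 | min(30, 28) = 28, so 28 January | 2 days early | 30 January |

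The rule is right when the event ends in the first-dose month. It fails when the event ends in a later month on a smaller day number.

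**How often, within the affected type of record.** Enumeration over every first-dose date in a 365-day year, every true onset day from first dose to the end of that month, and durations of 0 to 28 days (an assumption, not from the documents):

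- all on-treatment cases: 55,622 / 166,402 = 33% dated before first dose;
- cases ending in a later month: 55,622 / 104,342 = 53%;
- cases ending in the same month: 0 / 62,060;
- mean shift 8.2 days, maximum 30 days;
- if the end day is itself imputed to month end: 276 / 166,402 = 0.2%;
- with full dates compared: 0 / 166,402.

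A second set of assumptions is 30-day months, first-dose day uniform, onset uniform from first dose to month end, and exponential durations:

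| Mean duration (days) | Dated before first dose | Mean shift (days) |
|---|---|---|
| 5 | 31.1% | 16.4 |
| 10 | 41.0% | 13.8 |
| 20 | 45.6% | 12.1 |
| 30 | 46.8% | 11.6 |

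The mean shifts differ because the enumeration weights every onset day equally, so first doses early in the month count more, and because durations differ. Both settings give every event an end date. That the error exists does not depend on these assumptions; the percentages do.

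**Completely missing onset.** The year-only bullet names this case in its opening and contains an end-date exception. The next bullet covers the same case with no exception. Take an event with no onset recorded that ended before first dose. The last bullet dates its onset at first dose, after its own end; the exception would date it at its end. The exception is also keyed to the onset year, which such a record lacks, so the text does not settle which rule governs.

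**The case against.** The strongest reply is that the primary endpoint is already protected, and most of it stands.

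- **Treatment-emergent status.** A reader might infer that misdated events drop out of the primary endpoint. The documents do not establish this. Once 2.5.1 has been applied, no onset date is missing or partial, so the fallback in 2.6.12 has work to do only if it refers to the recorded date. An onset recorded as March, with first dose on 25 March and end on 3 April, cannot be placed before the first dose, so the event stays in. Related events stay in whatever their date. Still open is that 2.6.12 does not rule out using the imputed date.
- **Onset-time bands.** A reader might infer that the infection and neutropenia tables by onset time are distorted. They are not. The rule acts only in the first-dose month, so the true onset is within 30 days of first dose. The true, corrected and wrong dates all fall in the band up to 8 weeks.
- **Duration and linking.** SAP 6.1 plans no summary of event duration. Linking merges records of one preferred term within a subject, so subject incidence does not change.
- **Completely missing onset.** A reader might infer that such an onset is always set to the first dose date. The overlap with the preceding bullet makes this a conflict between two rules. It is also a rare case: with nonserious pre-dose events sent to medical history, essentially only serious events could end before first dose.
- **Charitable programming.** A programmer may compare full dates and then take the day. That avoids the error, but the text speaks of the day component and does not say this.

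**Conclusion.** The point holds as a wrong date rule with limited consequences. As written, the day-missing bullet gives a pre-dose onset to an on-treatment event that ends in a later month on a smaller day number than the first dose. What follows with certainty is a wrong onset date. It shows as a negative time in the infection Kaplan-Meier plot when such an event is the subject's first infection, as wrong dates in listings, and possibly as wrong dates in record linking.

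Loss of unrelated events from the treatment-emergent set, and so from the primary endpoint, is possible only if the imputed date is accepted as showing a pre-dose onset. The SAP leaves that open, but it is the less natural reading.

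The shares of 33%, or 31% to 47%, apply only to on-treatment events with a missing onset day in the first-dose month and a known end date. They are not shares of all adverse events. The documents give no count of such records. With 42 to 58 subjects planned and weekly visits in Cycles 1 and 2, the number is probably small. The rule is still worth correcting, because the fix is cheap and SAP section 3 says the data cut is meant to support a licence application.

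**What to change.** 1. **SAP 2.5.1, day missing.** When onset month and year equal those of first dose, impute the first dose date, unless the full AE end date is before the first dose date; in that case impute the AE end date.
2. **SAP 2.5.1, completely missing.** Take this case out of one of the two bullets so that it follows a single rule, with the same end-date exception and no test on an onset year that is not recorded.
3. **SAP 2.6.12.** State that an event with a missing or partial onset is excluded as pre-dose only if its recorded onset components or its end date show that it began before the first dose, and that the imputed onset is not used for this decision. The end date has to count: with first dose on 25 March, onset recorded as March and end on 10 March, the recorded onset alone would wrongly keep a finished pre-dose event.

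The cost is a few sentences in the SAP and a small programming change. No new data are needed.
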